In humans, the energy intake-independent effects of leptin have been assessed in only two studies. A single patient with acquired, generalized lipodystrophy was studied while taking leptin, and during leptin withdrawal, while maintaining constant energy intake²⁹. In this patient, blood glucose did not change during leptin withdrawal, a rise in serum insulin (indicative of worsening insulin resistance) was seen after four days, and a rise in triglycerides after seven days. Although based on a single subject, these data suggest that leptin's effects on both insulin resistance and lipids may be partly independent of energy intake in humans. Liebel's group studied the energy intake-independent effects of leptin in ten healthy subjects following 10% weight loss, a model of relative leptin deficiency¹¹. Subjects in the weight-reduced state were studied before and after five weeks of leptin replacement to pre-weight-loss levels, while maintaining constant energy intake. Leptin replacement resulted in an increase in energy expenditure to pre-weight-loss levels that appeared to be due to changes in skeletal muscle work efficiency, thyroid hormones, and catecholamines. Because these subjects did not have abnormalities of glucose or lipid metabolism, the energy intake-independent effects of leptin on these parameters were not examined.

Subject Eligibility Assessment and Enrollment

Inclusion Criteria

1. Age 14-70 years (children under age 18 will only be enrolled in the leptin-naïve arm of the study [Inclusion criterion 3b, below])
2. Clinically-significant lipodystrophy as summarized below:
 - a. Lipodystrophy identified by the study physician during physical examination as an absence of fat outside the range of normal variation.
 - b. Circulating leptin levels < 12.0 ng/mL in females and < 8.0 ng/mL in males
 - c. Presence of at least one of the following metabolic abnormalities:
 - i. Diabetes as defined by the 2007 American Diabetes Association criteria:
 1. Fasting plasma glucose \geq 126 mg/dL, or
 2. 2-hour plasma glucose \geq 200 mg/dL following a 75 gram 91.75 gm/kg) oral glucose load, or
 3. Diabetic symptoms with a random plasma glucose \geq 200 mg/dL.
 - ii. Fasting insulin $>30 \mu\text{U}/\text{mL}$
 - iii. Fasting hypertriglyceridemia $>200 \text{ mg/dL}$
 3. Either:

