- a. Leptin naïve, with plans to initiate leptin treatment during the current study. For the purpose of this study, “leptin naïve” will be defined as having received no exogenous leptin in the 4 months prior to study participation. Thus, subjects who previously received leptin therapy, discontinued, and wish to restart are eligible.

Or

- b. Leptin treated, meaning the subject has taken a stable dose of exogenous leptin for a minimum of 4 months prior to study entry (adults over age 18, only)

Exclusion Criteria

In leptin treated subjects only, the following exclusion criteria apply:

- 1. Poorly controlled diabetes at study entry (hemoglobin A1c $\geq 9\%$).
- 2. Poorly controlled hypertriglyceridemia at study entry (serum triglycerides $> 800 \text{ mg/dL}$).
- 3. Extreme hypertriglyceridemia prior to leptin (preleptin triglycerides greater than 2000 mg/dL).
- 4. History of chronic or recurrent acute pancreatitis (>1 episode), or a single episode of pancreatitis while receiving leptin treatment.
- 5. Lipase greater than the upper limit of normal (491 units/L) at study entry.
- 6. Known presence of neutralizing antibodies to leptin.

In all subjects (leptin treated and leptin naïve), the following exclusion criteria apply:

- 7. Known HIV infection or HIV-associated lipodystrophy.
- 8. History of diabetic ketoacidosis.
- 9. Active inflammatory disease (e.g. dermatomyositis).
- 10. Change in diabetes or lipid-lowering medications within the past 6 weeks.
- 11. Estimated glomerular filtration rate $< 30 \text{ mL/minute}$.
- 12. Current or recent (past 2 weeks) use of systemic glucocorticoids.
- 13. Inadequately controlled hypothyroidism (TSH < 0.4 or $>4 \text{ mIU/L}$) or change in thyroid medication in the past 8 weeks.
- 14. Pregnancy or breast-feeding.
- 15. Psychiatric disorder impeding competence or compliance.
- 16. Any medical condition or medication that will increase risk to the subject (e.g. ischemic heart disease, decompensated liver disease) or that will interfere with interpretation of study data (e.g. Cushing's syndrome).
- 17. Current alcohol or substance abuse.
- 18. Subjects who have a known hypersensitivity to E. coli derived proteins.
- 19. Subjects with acquired lipodystrophy and a hematologic abnormality such as neutropenia and/or lymphadenopathy.

Study Design and Statistical Analysis

Design

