This is an exploratory study of the energy-intake independent effects of leptin initiation and withdrawal in lipodystrophy. Preliminary data are not available to generate estimates of power for each outcome to be tested. The primary comparisons to be tested for each outcome of interest are results at the end of Period 1 versus the end of Period 2, analyzed separately for each group of subjects (leptin-naïve versus leptin treated). Thus, sample size calculations are based on paired, before and after, comparisons within each group of subjects. The data and references used for power calculations are shown in the table, below. Data in the table using the 10% weight loss model are given as percent change from pre-weight loss values, while data from lipodystrophy patients are given as absolute differences between leptin treated and untreated states. All calculations assumed a sample size of 10 and an alpha of 0.05, without correction for multiple comparisons. Because the standard deviations (SDs) of differences between on and off leptin conditions were not reported in publications, the SDs of the difference (used to calculate power for paired comparisons) was estimated in two ways: First, the SDs of differences are calculated by assuming that the SDs of on and off leptin reported in the literature are independent (Power 1 in the table). Second, a “worst-case scenario” was assumed that the SDs on and off leptin in the literature are perfectly positively correlated (Power 2 in the table). The first scenario is the commonly used method, while the second case is the most conservative calculation.

Outcome	Model	Duration of leptin	Off-leptin mean (SD)	On-leptin mean (SD)	Power 1	Power 2
Total energy expenditure ¹¹ (% Δ in kcal/day)	10% wt loss	5 wk	-22% (15.8)	-6% (4.7)	0.92	0.79
Skeletal muscle work efficiency ¹¹ (% Δ in kcal/min expended during exercise vs. at rest)	10% wt loss	5 wk	20% (12.6)	3% (2.5)	0.99	0.97
Resting energy expenditure ²⁴	lipodystrophy	4 mo	35.5 (8.2)	33.6 (6.7)	0.14	0.11
T3 ¹¹ (% Δ)	10% wt loss	5 wk	-9% (6.3)	3% (3.2)	0.99	0.99

T3 ⁴³ (nmol/L)	lipodystrophy	4 mo	124 (37)	114 (26)	0.18	0.13
T4 ¹¹ (% Δ)	10% wt loss	5 wk	-7% (7.9)	-1% (1.3)	0.77	0.66
fT4 ⁴³ (pmol/L)	lipodystrophy	4 mo	1.05 (0.15)	1.03 (0.15)	0.09	0.08
TSH ⁴³ (μU/mL)	lipodystrophy	4 mo	1.37 (0.37)	1.24 (1.1)	0.10	0.09
Norepinephrine ¹¹ (% Δ)	10% wt loss	5 wk	-12% (15.8)	-7% (12.6)	0.19	0.14
Epinephrine ¹¹ (% Δ)	10% wt loss	5 wk	-40% (35)	28% (47)	0.98	0.83

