Sympathetic nervous system tone ¹¹ (% Δ in mean ECG R-R interval after atropine + esmolol vs. atropine alone)	10% wt loss	5 wk	-25% (22.1)	1% (1.6)	0.98	0.97
Liver volume ²⁴ (cm ³)	lipodystrophy	4 mo	3055 (1051)	2433 (763)	0.45	0.29
Total body insulin sensitivity ³¹ (glucose infusion rate during clamp, mg*kg ⁻¹ *min ⁻¹)	lipodystrophy	1 mo	2.5 (0.79)	3.7 (1.1)	0.87	0.63
Total body insulin sensitivity ²⁵ (glucose infusion rate during clamp, mg*kg ⁻¹ *min ⁻¹)	lipodystrophy	4 mo	1.2 (0.35)	5.4 (1.6)	1	1
Hepatic insulin sensitivity ²⁵ (% suppression of endogenous glucose production during clamp)	lipodystrophy	4 mo	40 (10.4)	82 (8.7)	1	1
Fasting glucose ³¹ (mg/dL)	lipodystrophy	7 d	172 (20)	120 (12)	1	0.99
Fasting triglycerides ³¹ (mg/dL)	lipodystrophy	7 d	700 (272)	260 (98)	0.99	0.98
Fasting triglycerides ³¹ (mg/dL)	lipodystrophy	14 d	700 (272)	110 (38)	1	0.99
Rate of lipolysis ²⁵ (glycerol turnover, μmol*kg fat mass ⁻¹ *min ⁻¹)	lipodystrophy	4 mo	78 (36)	25 (7)	0.99	0.99

Based on these calculations, a sample size of 10 subjects in each group (leptin-naïve and leptin-treated) will provide greater than 80% power (in most cases greater than 95%) for the following primary and secondary outcomes:

Glucose Metabolism

1. Total body insulin sensitivity
2. Hepatic insulin sensitivity
3. Fasting plasma glucose

Lipid Metabolism

1. Rate of lipolysis
2. Fasting triglycerides

Energy Expenditure

1. Total energy expenditure
2. Skeletal muscle work efficiency

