Exploratory outcomes for which we anticipate greater than 80% power include epinephrine and sympathetic nervous system tone. Discrepant data exist for the effects of leptin on thyroid function (specifically, T3) based on the model used (lipodystrophy versus 10% weight loss), and this study should help to clarify whether this effect does or does not exist in lipodystrophy. We do not anticipate observing significant changes in resting energy expenditure; however, because this procedure is minimal risk, we feel that it will be important to document negative results for this outcome. Certain outcome measures, such as liver triglyceride (for which liver size was a proxy in the table, above), and insulin sensitivity, appear to progressively change over time with leptin replacement. For these outcomes, a 2 week intervention may be insufficient to observe statistically significant results. For other outcome measures, such as intramyocellular triglyceride, preliminary data on the short-term effects of leptin are not available, but effects, if present, are unlikely to be detectable by two weeks.

Therefore, in addition to obtaining data after 2 weeks of leptin withdrawal or initiation, we will restudy subjects in the leptin-naïve group 6 months (range is 5-9 months) after leptin initiation to look for changes that may not be detectable by 2 weeks.

Because some subjects may not complete the study, or may not have interpretable data for each outcome, we plan to enroll up to 20 subjects in each group in order to have 10 completers per group.

Statistical Methods for Data Analysis

Data will be analyzed separately for the leptin naïve and leptin treated subjects. This is done because the effects of leptin withdrawal after long-term treatment are likely to be different from the effects of leptin initiation after long-term deficiency.

Analysis of Primary Outcomes

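### The power claim for the leptin-treated (withdrawal) group rests on leptin-initiation effects and an unstated assumption that 14 days off leptin fully reverses them

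*Combined protocol and SAP*

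**What the plan says.** The Sample Size Justification states that "sample size calculations are based on paired, before and after, comparisons within each group of subjects" and that "All calculations assumed a sample size of 10 and an alpha of 0.05, without correction for multiple comparisons". One table serves both groups. Its rows give off-leptin and on-leptin means and SDs, indexed by a column headed "Duration of leptin", with entries of 7 days, 14 days, 1 month, 5 weeks or 4 months. No row or column describes time off leptin. The text below the table concludes that "a sample size of 10 subjects in each group (leptin-naïve and leptin-treated) will provide greater than 80% power" for seven named outcomes, including all three primary ones: total body insulin sensitivity, rate of lipolysis and total energy expenditure.

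Statistical Methods for Data Analysis keeps the groups apart because "the effects of leptin withdrawal after long-term treatment are likely to be different from the effects of leptin initiation after long-term deficiency". Under Leptin Withdrawal, the leptin-treated group goes without leptin on Days 0 to 13.

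The only withdrawal result at constant intake that the Introduction cites is one patient with acquired generalized lipodystrophy. In that patient "blood glucose did not change during leptin withdrawal", insulin rose after four days and triglycerides after seven. These data are not used in the table.

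**The concern.** The claim names the leptin-treated group, but the inputs describe the opposite intervention. The Introduction presents the sources behind the seven outcomes as studies of starting leptin: the weight-reduced healthy subjects before and after five weeks of leptin, the seven patients with generalized lipodystrophy followed from initiation, and the three patients studied after 3 to 8 months of replacement. The two remaining sources in the table have titles that describe leptin therapy.

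Carrying these effects over to withdrawal requires that they reverse, in full and within 14 days. The plan does not say so, and its reason for separate analyses points the other way. For the three primary outcomes the tabled effects took 5 weeks (energy expenditure), 1 or 4 months (insulin sensitivity) and 4 months (lipolysis) to measure.

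At stake is how a null withdrawal result is read. With a stated power above 80% it could pass for an adequately powered negative. The Rationale for Subject Selection describes this arm as above minimal risk, with no direct benefit to subjects, and justified by the knowledge it yields. An unsupported power statement matters most there.

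**Working it through.** **Inputs.** Means and SDs from the power table; n = 10; alpha = 0.05 (sidedness not stated).

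**Reproducing the plan.** The Power 1 column follows from a one-sided normal approximation with independent SDs:

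- SD_d = √(SD_off² + SD_on²)
- λ = |difference| × √10 / SD_d
- power = Φ(λ − 1.645)

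For total energy expenditure: SD_d = √(15.8² + 4.7²) = 16.48; λ = 16 × 3.162 / 16.48 = 3.07; power = Φ(1.42) = 0.92, as printed. All 19 rows reproduce within 0.02, so the table's arithmetic stands for the on/off differences it uses.

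**Sensitivity to the missing assumption.** Let 14 days of withdrawal produce a fraction f of the tabled effect with the same SD_d. Then power = Φ(fλ − 1.645), and the smallest f that keeps 80% power is (1.645 + 0.842) / λ. The documents give no value for f, so a range is shown.

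| Row | Difference | SD_d | λ | Plan's Power 1 | f = 1 | f = 0.75 | f = 0.5 | f = 0.25 | Smallest f for 80% |
|---|---|---|---|---|---|---|---|---|---|
| Total energy expenditure, 5 wk (primary) | 16 | 16.48 | 3.07 | 0.92 | 0.92 | 0.74 | 0.46 | 0.19 | 0.81 |
| Insulin sensitivity, 1 mo (primary) | 1.2 | 1.35 | 2.80 | 0.87 | 0.88 | 0.68 | 0.40 | 0.17 | 0.89 |
| Insulin sensitivity, 4 mo, three patients (primary) | 4.2 | 1.64 | 8.11 | 1 | 1.00 | 1.00 | 0.99 | 0.65 | 0.31 |
| Lipolysis, 4 mo (primary) | 53 | 36.67 | 4.57 | 0.99 | 1.00 | 0.96 | 0.74 | 0.31 | 0.54 |
| Muscle work efficiency, 5 wk | 17 | 12.85 | 4.19 | 0.99 | 0.99 | 0.93 | 0.67 | 0.27 | 0.59 |
| Hepatic insulin sensitivity, 4 mo | 42 | 13.56 | 9.79 | 1 | 1.00 | 1.00 | 1.00 | 0.79 | 0.25 |
| Fasting glucose, 7 d | 52 | 23.32 | 7.05 | 1 | 1.00 | 1.00 | 0.97 | 0.55 | 0.35 |
| Triglycerides, 7 d | 440 | 289.1 | 4.81 | 0.99 | 1.00 | 0.98 | 0.78 | 0.33 | 0.52 |
| Triglycerides, 14 d | 590 | 274.6 | 6.79 | 1 | 1.00 | 1.00 | 0.96 | 0.52 | 0.37 |

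**Smallest detectable change, n = 10, 80% power.** Two-sided paired t-test at 5% (noncentral t, 9 df): 0.996 SD of the paired difference. The table's one-sided z: (1.645 + 0.842) / √10 = 0.79 SD.

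**The case against.** The withdrawal arm is not without a calculation. The plan applies one paired on/off comparison to each group, and such a test does not depend on the direction of change. That is right: what is missing is support for using the same effect size, not the calculation.

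The plan says withdrawal effects are likely to be different, not smaller, and f is assumed here. Elsewhere it expects real worsening: Glucose Management anticipates poorer insulin sensitivity and possible hyperglycemia off leptin. This also stands, and it rules out the stronger reading, which a reader might infer, that the arm is underpowered.

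Two further inferences are tempting. One is that the single withdrawal patient shows little or late effect. The documents do not support this: insulin and triglycerides both rose within 14 days, and the unchanged glucose is one patient and one secondary outcome. The other is that exclusions such as "Poorly controlled hypertriglyceridemia at study entry" leave these subjects little scope to worsen. Good control on leptin does not limit a rise off it. The 2000 mg/dL pre-leptin cut-off lies (2000 − 700) / 272 = 4.8 SD above the tabled off-leptin mean. The risk section does tie that one criterion to rebound, but this does not make the tabled effect unattainable.

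Finally, the plan calls the study exploratory, says preliminary data are lacking for each outcome, and warns that two weeks may be too short for insulin sensitivity. These caveats help, but the last does not reach energy expenditure or lipolysis, and its remedy, the 6-month restudy, covers only the leptin-naïve group. The power sentence itself carries no qualification.

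**Conclusion.** The point holds as an unsupported power assumption, not an arithmetic error. The figure above 80% for the leptin-treated group is valid only if 14 days of withdrawal reverses most or all of the initiation effect, with the same variability. By the table's own method the required share is at least 0.81 for total energy expenditure, 0.89 for insulin sensitivity on the 1-month row (0.31 on the three-patient 4-month row) and 0.54 for lipolysis. At an assumed half effect these primary outcomes fall below 80%, except insulin sensitivity on the 4-month row (0.99). Hepatic insulin sensitivity, fasting glucose and 14-day triglycerides stay above it. True power in this arm cannot be computed from the documents, which contain no withdrawal mean change or SD.

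**What to change.** In the Sample Size Justification:

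1. Limit the statement of more than 80% power to the leptin-naïve group, and say that the table contains initiation data. This should not imply that the figures for that group are otherwise verified; the gap between the tabled durations and 14 days affects it too.
2. For the leptin-treated group, replace the claim with the smallest detectable change with 10 completers: about 1.0 SD of the paired difference at 80% power for the planned paired t-test (two-sided 5%). Note that the table's one-sided z method would give about 0.79 SD, so that the two are not confused. The change of method alone, at the full effect, moves energy expenditure from 0.92 to 0.78 and 1-month insulin sensitivity from 0.88 to 0.70, and should not be attributed to withdrawal.
3. State that a null withdrawal result does not exclude effects smaller than this.

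The change is wording only; design, sample size and conduct are untouched. The cost is that the power statement for the withdrawal arm becomes less favourable.

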This is a non-randomized, parallel group study. Two groups of patients aged 14 to 70 years with lipodystrophy will be studied: leptin naïve and leptin treated. Minors will only be included in the leptin naïve arm. All subjects will be stabilized on a weight maintenance diet for 5 days (Period 1). After this, leptin will be withdrawn from leptin treated subjects, and leptin will be initiated in leptin naïve subjects for a period of 14 days (Period 2). The same isocaloric diet will be continued throughout both Periods, permitting study of leptin's effects independent of energy intake.

All subjects will undergo metabolic testing on admission, at the end of Period 1, and throughout Period 2, to generate a detailed short-term time course of the effects of leptin initiation or withdrawal. At the end of Period 2, leptin will be continued in the leptin naïve subjects, and restarted in the leptin treated subjects. Repeat metabolic testing will be performed 6 months (ideally 5-9 months but may be extended to 12 months in foreign subjects) after leptin initiation in the leptin-naïve cohort to generate information on leptin's long-term effects.

Study Objectives

The primary aim of this study is to determine the energy intake-independent effects of leptin on energy metabolism in lipodystrophic subjects.

The null hypothesis is that, when caloric intake is fixed, leptin has no effects on energy metabolism.

The alternative hypothesis is that, when caloric intake is fixed, leptin does have measureable effects on energy metabolism.

The major aspects of energy metabolism to be studied are:

1. Lipid metabolism, including fasting lipids, lipolysis and fatty acid turnover, and ectopic lipid storage.
2. Glucose metabolism, including fasting glucose, endogenous glucose production, and insulin sensitivity
3. Energy expenditure, including total and resting energy expenditure, skeletal muscle work efficiency, and spontaneous physical activity

In addition, the effects of leptin on endocrine and autonomic function will be examined, including effects on the thyroid, gonadal, and adrenal axes, as well as blood pressure, body temperature, and heart rate.

Introduction

Leptin

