Measurements in each of the primary outcomes will be analyzed using the paired t-test (for normally distributed variables) or Wilcoxon paired test (for skewed variables) to test if there is any significant difference between the two study periods (on and off leptin) for each group (leptin naïve and leptin treated), respectively. In addition, mixed models incorporating baseline (pre-diet) parameters as covariates will be used to adjust for any effects of the inpatient, metabolic diet, independent of leptin's effects. For variables with more than 2 measurements during Period 2, repeated measure linear models (Mixed model or GLM) will be used to study the time effect, using pooled data from the 2 periods. Potential covariates to be explored in the model include: Age, sex, race, percent body fat, lean mass, body weight, type of lipodystrophy, and endogenous leptin level. To account for any deviation from the isocaloric protocol diet, actual caloric intake will be included as a covariate in mixed model analyses.

Additional correlations between variables within and between each of the major outcome categories (glucose metabolism, lipid metabolism, and energy expenditure) will be analyzed using either Pearson's correlation or simple linear regressions. These include the following:

1. Association between change in total body insulin sensitivity and changes in hepatic insulin sensitivity, fasting plasma glucose, and C-peptide
2. Association between change in rate of lipolysis, and changes in fasting triglycerides and fatty acid turnover
3. Association between insulin sensitivity and ectopic lipid stores, and rates of lipolysis and fatty acid turnover
4. Association between change in total energy expenditure and changes in resting energy expenditure, skeletal muscle work efficiency, spontaneous physical activity, thyroid function, catecholamines, and cardiac autonomic nervous system tone.

Analysis of Secondary and Exploratory Outcomes

Methods for analysis of secondary outcomes will be similar to those for primary outcomes. In addition, we will perform analysis to study the following associations between categories of outcome measures:

1. Association between the Ectopic Lipid measurements with Glucose and Lipid measurements
2. Association between the Endocrine measurements with Energy Expenditure measurements

Analysis of long-term data

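### The power table comes from a one-sided normal approximation and Power 2 carries the wrong correlation sign; under a two-sided paired t-test and independence, two primary outcomes have power 0.78 and 0.70, not 0.92 and 0.87

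*Combined protocol and SAP*

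**What the plan says.** The Sample Size Justification sets the basis of the calculation: "Thus, sample size calculations are based on paired, before and after, comparisons within each group of subjects". It adds: "All calculations assumed a sample size of 10 and an alpha of 0.05, without correction for multiple comparisons". Sidedness is not given.

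The SD of the paired difference was not available from the literature, so two versions were used. Power 1 is obtained by "assuming that the SDs of on and off leptin reported in the literature are independent (Power 1 in the table"). Power 2 supposes that "the SDs on and off leptin in the literature are perfectly positively correlated (Power 2 in the table"), and the text presents this as the worst case. It continues: "The first scenario is the commonly used method, while the second case is the most conservative calculation".

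After the table, the plan concludes that 10 subjects per group "will provide greater than 80% power (in most cases greater than 95%) for the following primary and secondary outcomes". The list names total body insulin sensitivity, hepatic insulin sensitivity, fasting glucose, lipolysis, fasting triglycerides, total energy expenditure and skeletal muscle work efficiency. Epinephrine and sympathetic tone are then added as exploratory outcomes with power above 80%.

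Under Analysis of Primary Outcomes, the test is a paired t-test (Wilcoxon if skewed) "to test if there is any significant difference between the two study periods (on and off leptin"). The alternative hypothesis under Study Objectives is that "leptin does have measureable effects on energy metabolism", with no direction given.

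**The concern.** Two things do not fit together. First, the printed powers look too high for a paired t-test with 10 pairs. With 9 degrees of freedom, estimating the SD costs noticeable power, and a non-directional test costs more. Second, for a paired difference, perfect positive correlation gives the smallest possible SD of the difference and hence the highest power. It cannot be the conservative case, yet Power 2 is printed lower than or equal to Power 1 in every row.

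Total energy expenditure and total body insulin sensitivity are two of the three primary outcomes. If the figures belong to a different test, the statement of more than 80% power with 10 completers lacks the support it claims for these two. A reader who takes the Power 2 label at face value would also conclude that positive within-subject correlation harms a paired design, when it helps.

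**Working it through.** **Inputs.** The sample size is n = 10 pairs and alpha is 0.05. Means and SDs are those in the power table. Total energy expenditure is -22 (15.8) off leptin and -6 (4.7) on leptin. The 1-month insulin-sensitivity row is 2.5 (0.79) off and 3.7 (1.1) on. The free T4 row is 1.05 (0.15) off and 1.03 (0.15) on.

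**Formulas.** D = |on - off|. SDdiff(r) = sqrt(SDoff² + SDon² - 2·r·SDoff·SDon), so r = 0 gives sqrt(SDoff² + SDon²), r = -1 gives SDoff + SDon, and r = +1 gives |SDoff - SDon|. The standardised shift is δ = D·sqrt(10)/SDdiff. One-sided z power is Φ(δ - 1.645). Two-sided paired t power comes from the noncentral t on 9 df with noncentrality δ and critical value 2.262.

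**Step 1: reproduce the printed table.** Total energy expenditure at r = 0: D = 16, SDdiff = sqrt(15.8² + 4.7²) = 16.48, δ = 3.07, Φ(3.07 - 1.645) = 0.923 (printed 0.92). At r = -1: SDdiff = 20.5, δ = 2.47, power 0.795 (printed 0.79). Insulin sensitivity at 1 month, r = 0: D = 1.2, SDdiff = 1.354, δ = 2.80, power 0.876 (printed 0.87). At r = -1: SDdiff = 1.89, δ = 2.01, power 0.642 (printed 0.63).

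Largest departure from the printed values over 19 rows and both columns, with r = 0 for Power 1 and r = -1 for Power 2:

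| Method | Largest deviation |
|---|---|
| One-sided z | 0.012 |
| One-sided t | 0.064 |
| Two-sided z | 0.122 |
| Two-sided t | 0.209 |

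Only the one-sided z fits.

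**Step 2: test the Power 2 label.** In the free T4 row the SDs are equal, so r = +1 gives SDdiff = 0 and power 1.00; 0.08 is printed. At r = -1, SDdiff = 0.30 and one-sided z power is 0.076, which matches. Other rows at r = +1 (one-sided z) against printed Power 2: resting energy expenditure 0.99 against 0.11; T3 in lipodystrophy 0.89 against 0.13; norepinephrine 1.00 against 0.14. The printed column is r = -1.

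**Step 3: recompute for a two-sided paired t-test, n = 10.**

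| Row | Printed Power 1 / Power 2 | Two-sided t, r = 0 / r = -1 |
|---|---|---|
| Total energy expenditure | 0.92 / 0.79 | 0.78 / 0.60 |
| Insulin sensitivity, 1 month | 0.87 / 0.63 | 0.70 / 0.43 |
| Insulin sensitivity, 4 months | 1 / 1 | 1.00 / 1.00 |
| Hepatic insulin sensitivity | 1 / 1 | 1.00 / 1.00 |
| Fasting glucose | 1 / 0.99 | 1.00 / 0.995 |
| Triglycerides, 7 days | 0.99 / 0.98 | 0.99 / 0.92 |
| Triglycerides, 14 days | 1 / 0.99 | 1.00 / 1.00 |
| Lipolysis | 0.99 / 0.99 | 0.98 / 0.93 |
| Skeletal muscle work efficiency | 0.99 / 0.97 | 0.96 / 0.89 |
| Epinephrine | 0.98 / 0.83 | 0.90 / 0.65 |
| Sympathetic tone | 0.98 / 0.97 | 0.91 / 0.87 |

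Simulation with 400,000 runs agrees: 0.779 and 0.596 for total energy expenditure, 0.704 and 0.435 for 1-month insulin sensitivity. At the stated r = +1 the two rows would have power 0.98 and 1.00.

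**Step 4: which correction matters.** At r = 0, changing only to two-sided z gives 0.866 and 0.800. Changing only to one-sided t gives 0.882 and 0.826. Both changes are needed to fall below 80%.

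**Step 5: sensitivity to correlation.** The documents give no on/off correlation. Over an assumed range r = 0 to 0.5, two-sided t power is 0.78 to 0.89 for total energy expenditure and 0.70 to 0.93 for 1-month insulin sensitivity. It reaches 80% at r of about 0.09 and 0.22. Under independence, 80% needs 11 completers (0.826) and 13 completers (0.834).

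**The case against.** The strongest reply is that the plan never declares a two-sided test. Correcting only what it states outright, a paired t-test, leaves 0.88 and 0.83, both above 80%. That is true, and the shortfall does depend on reading the test as two-sided. But a search for any difference with a non-directional alternative is naturally two-sided, nothing declares a one-sided test, and even the one-sided t does not return 0.92 and 0.87.

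A second reply is that independence is pessimistic for repeated measurements on the same person, so a modest positive correlation restores 80%. That also stands. It limits the conclusion to the table and the statement drawn from it.

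Third, the label error is one word. The descriptions as worst case and most conservative fit the numbers printed, and the slip does not flatter them. Agreed, but the stated assumption still contradicts the calculation.

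Fourth, the lists above 80% appear to rest on Power 1, since total energy expenditure is listed despite a printed Power 2 of 0.79. On that column epinephrine stays at 0.90, so its listing survives. Only the printed Power 2 figure of 0.83 changes, to 0.65.

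Finally, the study is called exploratory, and the same section already warns that 2 weeks may be too short for insulin sensitivity. That caveat is useful, but it does not extend to total energy expenditure and corrects neither the method nor the label.

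**Conclusion.** The concern holds. The printed table is a one-sided 5% normal approximation rather than the power of the planned paired t-test, and Power 2 was computed at correlation -1 while the text says +1. Both follow from the table's own figures.

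On the two-sided reading and the plan's independence assumption, the claim of more than 80% power fails narrowly for total energy expenditure (0.78) and more clearly for the 1-month insulin-sensitivity row (0.70). The insulin-sensitivity listing then rests on the 4-month row alone. That row comes from a mechanistic study which the Introduction (Leptin in lipodystrophy) describes as three patients, whereas the primary contrast here is at about 2 weeks. Lipolysis, the third primary outcome, and the listed secondary outcomes remain above 80% in both columns.

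The correction is worth making but limited in effect. The shortfall rests on an inferred two-sided test and on zero correlation, and it does not establish that the trial is underpowered.

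**What to change.** - State the test used for power and its sidedness.
- Recompute both columns with the noncentral t on 9 df, two-sided unless a one-sided test is declared and justified.
- Relabel Power 2 as perfect negative correlation, with SDdiff = SDoff + SDon.
- Qualify the statement of more than 80% power: total energy expenditure 0.78 under independence; insulin sensitivity 0.70 on the 1-month row, with the listing supported only by the 4-month, three-patient row; epinephrine 0.65 under the Power 2 SD.
- Optionally, show power over an assumed correlation range, and link the list of powered outcomes to the existing caveat about a 2-week intervention.

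The cost is one recalculated table, one corrected label and a few sentences. The stated power becomes less favourable. The enrolment ceiling of 20 per group, the target of 10 completers, the tests and the endpoints are unchanged.
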